^t **Disease assessments during follow-up period:** are only required for patients with PR or better who have discontinued treatment for reasons other than disease progression and have not yet started treatment with another anti-cancer therapy. Patients will be followed every month for progression during this period. Disease assessments required every month include evaluation of serum M-protein, serum free light chains, and serum immunoglobulins. A bone skeletal survey and PET/CT/MRI are only required if clinically indicated to confirm response or progression according to IMWG criteria. Disease assessments are not required in the follow-up period by this study for patients who have discontinued treatment due to progression or once patients starts treatment with another anti-cancer therapy. For patients who are off study due to disease progression, they will receive a phone call at minimum per study every 4 weeks for one year post last study drug treatment to assess survival

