- Skeletal survey (X-ray; including skull, rachis, all long bones, pelvis and chest), if clinically indicated.

Post-treatment/ Follow-Up

Each subject will be followed until 1 year after his/her last dose of study treatment, until death or withdrawal of consent for study participation, whichever occurs first. The end of study is defined as when all subjects have completed either at least 1 year of follow-up, or until death or withdrawal of consent for study participation, whichever occurs first.

For subjects with serologic evidence of resolved HBV infection (i.e., positive Anti-HBs or positive Anti-HBc) at Screening, HBV DNA testing by PCR must be performed locally. For these patients, HBV DNA testing PCR must be done Q12W during treatment, at the End of Treatment Visit, and Q12W for up to 6 months after the last dose of study treatment.

After confirmed disease progression or the start of a new treatment for multiple myeloma, subjects will at minimum be contacted by telephone every 12 weeks for follow- up assessments (ie, other malignancies, next-line therapy, PD on next-line therapy, and survival, as applicable) until death, withdrawal of consent for study participation, or the end of the 1 year follow-up period, whichever occurs first. Following disease progression on the next-line therapy, subjects will only be followed for survival.

If the information on other malignancies, next-line therapy, PD on next-line therapy, and survival is obtained via telephone contact, written documentation of the communication must be available for review in the source documents. If the subject has died, the date and cause of death will be collected and documented on the CRF.

Investigators may recontact the subject to obtain long-term follow-up information regarding the subject's safety or survival status as noted in the ICF.

Subjects will be instructed that study drug (ie, daratumumab) will not be made available to them after they have completed/discontinued study drug and that they should return to their primary physician to determine standard of care.

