Disease progression must be consistently documented using the criteria in table in [Section 7.1.1](#). Disease progression based on 1 of the laboratory tests alone must be confirmed by at least 1 repeat investigation. Clinical judgment should prevail; however, repeat assessments after 1 to 3 weeks can be used as a general guideline. Disease progression based on imaging, bone marrow plasma cell percentage, or hypercalcemia (not attributable to any other cause) do not need to be confirmed. Bone marrow biopsy to assess morphology (aspirate and biopsy) at the time of progression will be at the discretion of the individual provider and not required by the study.

For subjects who discontinue study treatment before disease progression, disease evaluations should continue to be performed as described every 4 weeks until confirmed disease progression, death, the start of a new treatment for multiple myeloma, withdrawal of consent for study participation, or the end of study, whichever occurs first.

Methods of Response Evaluation

Response evaluation will include:

- M-protein quantification (serum and 24-hr urine)
- Serum free light chain (FLC) levels
- Bone marrow biopsy/aspiration (not required)

Myeloma Protein Measurements in Serum and Urine

Blood and 24-hour urine samples will be collected for serum quantitative IgGs, serum and urine M-protein measurements, serum and urine IFE measurements, and serum FLC assay in screening phase (within 28 days of first azacitidine administration). If urine samples cannot be collected, then serum markers will be used alone. Serum quantitative immunoglobulins, serum M-protein measurements, serum IFE, and serum FLC assay will be performed on Cycle 1 Day -7 (prior to first azacitidine dose), unless screening disease evaluation labs were performed within 14 days prior to this first azacitidine administration, and every subsequent cycle on D1 starting cycle 2 (disease evaluation labs do not need to be repeated on Cycle 1 Day 1) until off study and at EOT.

Blood (and 24-hour urine, as determined by the treating physician) samples for disease evaluation will be collected until the development of confirmed disease progression. Progression of disease based on serum markers will need to be confirmed by at least 1 repeat investigation. Progression of disease based on urine markers does not need to be confirmed. Clinical judgment should prevail; however, repeat assessments after 1 to 3 weeks can be used as a general guideline.

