8.2 Analyses

Analyses Population

Analysis of primary and secondary efficacy variables will be based on the response-evaluable population, which includes all subjects who have measurable disease and received at least 2 cycles of study treatment, and have at least 2 efficacy evaluation assessments. All safety analyses for AEs will be based on the safety analysis set, which includes all subjects who receive at least 1 cycle of study treatment.

Safety Analysis

The study will begin with accrual of 6 patients in a safety run-in with interim safety analysis occurring after these 6 patients have completed at minimum Cycle 1 and further accrual stopped until safety analysis completed. If $\geq 2/6$ patients in the safety cohort have dose limiting toxicities (DLTs) as defined in [Section 5.4](#), then further study accrual will be halted until the study PI, co-investigators, and the DSMC can review the data, and determine whether the study should continue, be amended with a lower starting dose of azacitidine, or be closed to further accrual. Toxicities will be monitored throughout the study using CTCAE 5.0 criteria. Though we do not expect to observe DLTs during the study period, formal safety bounds based upon monitoring DLTs as defined in [Section 5.4](#) will guide decisions about early stopping due to potential safety concerns. A Pocock-type sequential boundary⁵⁹ will be used to monitor dose-limiting toxicities with the aim of keeping the probability of early stopping at around 90% if the true underlying toxicity rate is 25%. If the number of dose-limiting toxicities is equal to or exceeds the stopping boundaries detailed in the following table at any point in the study, then accrual to the study will be suspended until the study PI, co-investigators, and the DSMC can review the data, and determine whether the study should continue, be amended with a lower starting dose of azacitidine, or be closed to further accrual. With a toxicity rate of 25%, the expected number of enrolled patients before stopping for excessive toxicities is 6.5.

Table 8-1. Table: Safety monitoring bounds for DLTs

Number of subjects	Stopping boundary
6-9	≥ 2
10-14	≥ 3
15-18	≥ 4
19-23	≥ 5

Adverse Events

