Secondary endpoints for efficacy will be assessed using duration of response (DOR), progression-free survival (PFS), and overall survival (OS). DOR is defined as the duration from the date of initial documentation of a response (PR or better) according to the IMWG criteria to the date of first documented evidence of progressive disease according to the IMWG criteria or death due to PD whichever occurred first. DOR for subjects who have not progressed will be censored at the last disease evaluation before the start of any subsequent anti-myeloma therapy. PFS which is defined as the duration from the date of first dose of study treatment to the date of first documented evidence of progressive disease or death, whichever occurs first. Participants without a disease assessment will be censored at the date of first study treatment received. OS will be calculated as the time from the first dose of study treatment until death from any cause. Participants who have not died will be censored at the last time the participant was known to be alive. Distributions of DOR, PFS, and OS will be summarized using the Kaplan-Meier estimator. For each secondary efficacy endpoint, median even-free survival will be reported and the corresponding 95% confidence interval will be calculated using Brookmeyer and Crowley method.

Correlative Studies Analysis

CD38 regulation by azacitidine (Secondary Endpoint)

Change in CD38 surface expression in MM patients treated with azacitidine will be summarized using descriptive statistics and tested using the one-sample t-test. Two-sided p-value less than 0.05 will be considered statistically significant. The proportion of patients with at least a 1.5 fold increase in CD38 expression after one cycle of azacitidine treatment will also be reported. This phase II sample size of 23 will provide >99% statistical power to detect a fold change of 1.965 (SD: 0.299) in CD38 surface expression of MM patients treated with azacitidine based on a one-sample t-test at a two-sided type I error rate of 0.05. This estimated change in CD38 surface expression was calculated from our preliminary pre-clinical data. The association between the fold change in CD38 expression post azacitidine treatment and depth of response and duration of response will also be evaluated using logistic regression, linear regression methods, and Spearman's correlation coefficient, as appropriate.

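### Calendar footnote t limits progression follow-up after treatment to responders, while Section 7.1 requires it for every patient who stops before progression; if sites follow the calendar, PFS is biased upward

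*Combined protocol and SAP*

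**What the plan says.** All references are to the combined protocol and SAP.

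- **Section 6.1, footnote t.** Disease assessments in the follow-up period "are only required for patients with PR or better who have discontinued treatment for reasons other than disease progression" and who have not begun another anti-cancer therapy.
- **Section 7.1, Assessment of Disease Progression or Response.** "For subjects who discontinue study treatment before disease progression, disease evaluations should continue to be performed as described every 4 weeks". This runs until confirmed progression, death, new myeloma treatment, withdrawal of consent or end of study. Response is not a condition.
- **Section 7.1, Methods of Response Evaluation.** Blood (and, at the physician's choice, urine) "samples for disease evaluation will be collected until the development of confirmed disease progression", again regardless of response.
- **Section 8.2, PFS.** The endpoint is "the duration from the date of first dose of study treatment to the date of first documented evidence of progressive disease or death". The earlier of the two events counts. It is not restricted to responders. The only PFS censoring rule is "Participants without a disease assessment will be censored at the date of first study treatment received".
- **Section 8.2, DOR.** By contrast, "DOR for subjects who have not progressed will be censored at the last disease evaluation before the start of any subsequent anti-myeloma therapy".
- **Section 8.2, population.** Efficacy analyses use patients with measurable disease who "received at least 2 cycles of study treatment, and have at least 2 efficacy evaluation assessments".
- **Section 6.3, follow-up.** "Each subject will be followed until 1 year after his/her last dose of study treatment", or until death or withdrawal of consent. Telephone contact is specified only after progression or new therapy (Section 6.3) or for patients off study for progression (footnote t).

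**The concern.** Take a patient with stable disease who stops without progression. Section 3.4 allows this for several reasons, including an unacceptable adverse event, intercurrent illness, non-compliance and the patient's own decision. Section 7.1 keeps that patient under 4-weekly evaluation; footnote t schedules nothing after the end-of-treatment visit. A site cannot treat both as the full requirement, and Section 6.3 points sites to the calendar for the timing of procedures.

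PFS pools responders and non-responders. If only non-responders lose follow-up, censoring is tied to prognosis. The Kaplan-Meier estimator then represents the censored patients by those still at risk, a group that becomes increasingly rich in responders. The curve rises even if stopping treatment does nothing to a patient's hazard, and rises further if progression speeds up after stopping. The 1-year PFS named in the synopsis objectives would be read as better than it is. If some sites or staff follow Section 7.1 and others the calendar, follow-up also differs between patients for no planned reason.

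**Working it through.** **1. The plan's own figure.** The documents plan no PFS value. The figure that can be checked is the ORR design (Section 8.1): continue if at least 2 of 13 respond, reject if at least 5 of 23 respond, 8% against 33%. The rejection probability is the sum over x = 2 to 13 of P(X1 = x) × P(X2 ≥ 5 − x), with X1 ~ Bin(13, p) and X2 ~ Bin(10, p). It is 0.0302 at p = 0.08 and 0.9031 at p = 0.33, so the stated 5% and 90% reproduce. Nothing below alters them.

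**2. Who differs between the rules.** Only patients with less than PR who stop without progression and have not died, withdrawn or started new therapy. Expected non-responders at 33% ORR: 23 × 0.67 = 15.4.

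**3. Who enters the PFS analysis.** Cycle 1 runs from day -7 to day 28, so two cycles take 35 + 28 = 63 days, or 63/30.44 = 2.07 months. A patient who stops earlier is excluded under Section 8.2, not censored.

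**4. Illustration.** From the documents: ORR 33% (Section 8.1), and scenario medians for non-responders of 2.6 months (oral azacitidine combination, Section 1.2) and 3.5 months (first regimen after a CD38 antibody, Section 1.3). Both describe whole cohorts and are only borrowed here.

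Assumptions not in the documents:
- exponential PFS, with responder median 11 months
- 10-30% of non-responders assigned a stop, uniform over 2.1-5 months, which counts only if it precedes progression
- hazard after stopping 1 or 2 times the earlier hazard
- no deaths captured after stopping
- the Section 8.2 population approximated by patients progression-free at 63 days

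*Patients affected* = 15.41 × q × [exp(−2.1h) − exp(−5h)] / (2.9h), with h = ln 2 / median and q the share assigned a stop.
- Median 2.6, q = 0.10: h = 0.2666; 15.41 × 0.10 × (0.5713 − 0.2637)/0.7731 = 0.61.
- Median 3.5, q = 0.30: h = 0.1980; 15.41 × 0.30 × (0.6597 − 0.3715)/0.5743 = 2.32.

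*True 1-year PFS when the hazard is unchanged*, median 3.5, given progression-free at 2.07 months: [0.33 × exp(−12 ln 2/11) + 0.67 × exp(−12h)] / [0.33 × exp(−2.07 ln 2/11) + 0.67 × exp(−2.07h)] = 0.2171/0.7343 = 29.6%. The denominator also gives 23 × 0.734 = 16.9 evaluable patients.

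*Calendar rule.* Simulation of 1,000,000 patients per scenario, Kaplan-Meier with affected patients censored when they stop:

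| Non-responder median (months) | q | Hazard after stop | Affected of 23 | 1-year PFS, full follow-up | 1-year PFS, calendar | Gap (points) |
|---|---|---|---|---|---|---|
| 2.6 | 10% | ×1 | 0.6 | 27.0% | 28.0% | about 1 |
| 2.6 | 30% | ×2 | 1.8 | 25.9% | 30.2% | about 4 |
| 3.5 | 10% | ×1 | 0.8 | 29.6% | 30.5% | about 1 |
| 3.5 | 20% | ×2 | 1.5 | 28.2% | 31.3% | about 3 |
| 3.5 | 30% | ×1 | 2.3 | 29.6% | 32.4% | about 3 |
| 3.5 | 30% | ×2 | 2.3 | 27.5% | 32.4% | about 5 |

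Over all 12 combinations (q of 10, 20 and 30%) the gap ran from 0.8 to 4.9 points, always upward.

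**5. What Section 7.1 would recover.** Its evaluations also end at new therapy. With an assumed median of 1 month from stopping to new therapy, and censoring at that point, 1-year PFS under Section 7.1 was only 0.1 to 1.7 points below the calendar value in the same 12 scenarios. Slower starts of new therapy would recover more.

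**The case against.** The strongest case against is about size and certainty, and most of it stands.

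- **The effect is conditional.** It arises only if footnote t is followed in preference to Section 7.1. A reader might infer that PFS in this trial is biased as a matter of fact. The documents establish a contradiction, and a bias under one of its two readings.
- **Early stops do not count.** A reader might run the calculation over all enrolled patients with stops from the first weeks and obtain a larger effect. Section 8.2 removes anyone without two cycles and two assessments from the PFS set. That is a separate selection question, not censoring.
- **Toxicity.** A reader might infer that toxicity is the main reason non-responders will stop. Section 3.4 lists an adverse event as one reason among several, the synopsis names toxicity and progression without ranking them, and Section 8.2 says DLTs are not expected.
- **Partial safeguards exist.** There is a disease assessment at end of treatment (Section 6.3), assessment whenever progression is suspected (Section 6.1), and one year of follow-up after the last dose. Death is a PFS event, so deaths that are captured reduce the bias.
- **Precision is low anyway.** With about 17 evaluable patients and a 1-year PFS near 30%, the 95% half-width is roughly 1.96 × √(0.3 × 0.7/17) = 0.22, well above the gaps shown. PFS is descriptive and untested.

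None of this removes the contradiction or changes the direction. Low precision does not excuse an avoidable bias, and assessments not made on schedule cannot be recovered at analysis.

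**Conclusion.** The point holds as a protocol inconsistency with a conditional effect on a secondary endpoint. Footnote t and Section 7.1 cannot both be followed for a patient with less than PR who stops without progression. Under the calendar, that patient has no scheduled progression assessment after the end-of-treatment visit. Censoring there is an inference from the missing PFS rule, but it is the natural default. The bias is upward.

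The size is not derivable from the documents. On the assumptions listed in the working, about 0.6 to 2.3 of 23 enrolled patients are affected and 1-year PFS is overstated by about 1 to 5 points. It would be wrong to infer that aligning the passages removes all of this: follow-up under Section 7.1 also stops at new therapy, so only part is recovered. It would equally be wrong to carry the point to the primary result. ORR, the stage rules and the sample size are unaffected, and DOR is essentially unaffected because responders are followed under both rules. Severity: minor to moderate.

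**What to change.** 1. Amend footnote t of Section 6.1 to match Section 7.1. Every patient who stops treatment without progression, regardless of response, has serum M-protein, free light chains and immunoglobulins every 4 weeks until confirmed progression, death, new anti-myeloma therapy, withdrawal of consent or end of study.
2. Add to the PFS paragraph of Section 8.2 that patients alive without progression are censored at their last disease assessment before any new anti-myeloma therapy.

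The cost is a footnote edit, one sentence in the analysis section, and monthly routine blood tests for a few extra patients. Make the change before affected patients come off treatment.

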Study Description	This is a single-arm, 2-stage, phase II study of the safety and efficacy of daratumumab in combination with azacitidine and dexamethasone in relapsed/refractory multiple myeloma (RRMM) patients who have previously been exposed to daratumumab. Based on pre-clinical data we hypothesize that azacitidine, by upregulating the expression of CD38, can potentially increase the antibody-dependent cell-mediated cytotoxicity and efficacy of daratumumab on multiple myeloma cells and help reverse daratumumab resistance. This study aims to assess the efficacy and safety of daratumumab and azacitidine in relapsed refractory multiple myeloma.
Phase of Study	Phase 2
Investigational Products	Daratumumab and Azacitidine
Study population	Patients \geq 18 years of age with relapsed or refractory multiple myeloma (RRMM) who have progressed on \geq 2 lines of prior therapy, including an immunomodulatory drugs (IMiD) and proteasome inhibitor, and have previously been treated with daratumumab, with most recent daratumumab treatment being at least 6 months prior to enrollment to allow for CD38 normalization.
Primary Objective	
 To evaluate the efficacy, as determined by the overall response rate (ORR) of daratumumab in combination with azacitidine and dexamethasone in RRMM patients who have previously been exposed to daratumumab
Secondary Objectives	
 To evaluate duration of response per IMWG response criteria. To assess the safety and toxicity of azacitidine in combination with daratumumab and dexamethasone To assess the 1-year OS and PFS of daratumumab in combination with azacitidine and dexamethasone To evaluate the change in CD38 expression on plasma cells induced by azacitidine in patients with RRMM and correlate this change with depth and duration of response

Sample Size	
Simon's minimax two-stage design will be used.
 
The overall study (including the safety lead-in) plans to enroll 23 patients.
 
Safety Lead In: We expect to enroll 6 patients overall in the safety lead-in.
 
Stage 1: We expect to enroll a total of 13 patients during Stage 1 (including the 6 patients enrolled in the safety lead-in). Depending on the clinical response in Stage 1, Stage 2 will commence.
 
Stage 2: If there is ≥ 2 responses in 13 patients the study will enroll an additional 10 patients.
 
If there is ≤ 1 response in 13 patients the study will be stopped.

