3.4 Duration of Treatment

In the absence of treatment delays due to adverse events, treatment may continue indefinitely or until:

- Disease progression which requires discontinuation of the study treatment;
- Inter-current illness that prevents further administration of treatment;
- Unacceptable adverse event(s);
- Participant decides to withdraw from the study;
- Significant participant non-compliance with protocol;
- If the participant meets an exclusion criterion (either newly developed or not previously; or, recognized) that precludes further study participation
- General or specific changes in the participant's condition render the participant unacceptable for further treatment in the judgment of the investigator.

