3.5 Duration of Follow Up

Each subject will be followed until 1 year after his/her last dose of study treatment, until death or withdrawal of consent for study participation, whichever occurs first. The end of study is defined as when all subjects have completed either at least 1 year of follow-up, or until death or withdrawal of consent for study participation, whichever occurs first. Further details regarding the long-term follow-up phase are detailed in [Section 6.3.3](#).

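### Calendar footnote t limits off-treatment disease assessment to patients with PR or better, while Section 7.1 requires it for everyone who stops before progression; the survival-call rules also disagree.

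*Combined protocol and SAP*

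**What the plan says.** Two texts set the disease-assessment rule after treatment stops.

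- Section 6.1, footnote t: assessments "are only required for patients with PR or better who have discontinued treatment for reasons other than disease progression" and who have not started another anti-cancer therapy. These are monthly.
- Section 7.1, Assessment of Disease Progression or Response: "For subjects who discontinue study treatment before disease progression, disease evaluations should continue to be performed as described every 4 weeks". This runs until confirmed progression, death, new myeloma treatment, withdrawal of consent or end of study. There is no response condition.

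Two texts set the survival-call rule.

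- Footnote t: "For patients who are off study due to disease progression, they will receive a phone call at minimum per study every 4 weeks". These calls end a year after the last study drug.
- Section 6.3, Post-treatment/Follow-Up: "After confirmed disease progression or the start of a new treatment for multiple myeloma, subjects will at minimum be contacted by telephone". The interval is 12 weeks, and response does not matter.

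Over both stands a general duty in Section 3.5, repeated in Section 6.3: "Each subject will be followed until 1 year after his/her last dose of study treatment", or until death or withdrawal of consent. That sentence gives no contact interval. Section 6.3 adds an option: "Investigators may recontact the subject to obtain long-term follow-up information".

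**The concern.** Stopping before progression is foreseen. Section 3.4 lists several reasons, among them "Inter-current illness that prevents further administration of treatment" and unacceptable adverse events. A patient who stops for such a reason without having reached PR falls under Section 7.1 but outside footnote t.

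The Abstract lists as a secondary objective "To assess the 1-year OS and PFS of daratumumab in combination with azacitidine and dexamethasone". PFS in Sections 2.3 and 8.2 runs from first dose to progression or death and is not confined to responders. If no assessment is scheduled after treatment stops, a later progression may never be dated. Section 8.2 gives a PFS censoring rule only for participants with no disease assessment at all. A patient with on-treatment assessments and none afterwards would probably be censored near the last of them. Patients who stop early without a response may differ in prognosis from those who stay on, so such censoring could be informative.

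**Working it through.** The plan gives no figure on this point to reproduce. The check sets the rules side by side by patient state after treatment stops.

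| State off treatment | Disease assessment, footnote t | Disease assessment, Section 7.1 | Survival call, footnote t | Survival call, Section 6.3 |
|---|---|---|---|---|
| PR or better, not progressed, no new therapy | monthly | every 4 weeks | none | none |
| Below PR, not progressed, no new therapy | **none** | every 4 weeks | none | none |
| New therapy started, not progressed | none | ends | none | every 12 weeks |
| Progression confirmed | none | ends | every 4 weeks | every 12 weeks |

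Three things follow.

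1. The disease-assessment conflict is confined to the second row. Responders are covered under either text.
2. In that same row no fixed-interval survival call applies under either text. If Section 7.1 governs, the 4-weekly evaluation supplies the contact. If footnote t governs, nothing does at a fixed interval.
3. The last row shows a separate conflict: 4-weekly or 12-weekly calls after progression. The third row shows that the trigger differs too, since only Section 6.3 counts new therapy.

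**How many patients.** The documents do not say how many will stop below PR and before progression. An illustration uses N = 23 and the Section 8.1 response rates.

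- Expected below PR: 23 × (1 − 0.33) = 15.4 at an ORR of 33%; 23 × (1 − 0.08) = 21.2 at 8%. This is the ceiling on the group footnote t could leave out.
- Table 1-1 reports stopping for adverse events in 10% (bortezomib), 13% (lenalidomide) and 16% (pomalidomide) of patients on daratumumab combinations. Lowest product: 15.4 × 0.10 = 1.5. Highest: 21.2 × 0.16 = 3.4.
- For daratumumab monotherapy the same table reports 4% (integrated analysis) and none (subcutaneous study): 0 to 21.2 × 0.04 = 0.8.

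The illustration assumes that these rates carry over to this regimen and are independent of response. It omits the other Section 3.4 reasons for stopping. It overstates the number if non-responders mostly progress first, start new therapy soon, or stop before the 2 cycles that the Section 8.2 response-evaluable population requires.

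**The case against.** The strongest reply is that follow-up is already owed. Sections 3.5 and 6.3 oblige the study to follow every subject for a year, and Section 6.3 requires date and cause of death on the CRF. Adverse-event rules add contact beyond 30 days: footnote f of the calendar, Section 7.5 and the SAE follow-up text in Section 7.7 require certain events to be followed to resolution or stabilization. Patients who stop for toxicity are the ones most likely to have such events. Non-responders are also unlikely to stay long in the uncovered state: the protocol cites median PFS of 2.6 months with oral azacitidine, lenalidomide and dexamethasone (Section 1.2) and 3.5 months on the first regimen after CD38-antibody relapse (Section 1.3).

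Much of this stands, and it rules out some stronger readings.

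- A reader might infer that non-responders who stop early never receive a survival call. They do under Section 6.3, once progression is confirmed or new therapy starts.
- A reader might infer that their OS would be lost. Survival status is still owed for one year; what is missing is a contact interval. The residual concern is mainly the dating of progression.
- A reader might infer that the Section 5.5 wording about leaving the study after certain toxicities ends follow-up. Footnote t itself telephones patients it describes as off study, and Sections 3.5 and 6.3 end follow-up on death or withdrawal of consent, not on a toxicity rule. No real conflict is shown.

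The reply does not remove the disagreement between footnote t and Section 7.1. Adverse-event follow-up is event-driven and includes no disease evaluation. The Section 6.3 trigger needs confirmed progression, which footnote t schedules no assessment to detect. Section 7.1 wants laboratory-only progression confirmed by a repeat test, so a first rise at the end-of-treatment visit could stay unconfirmed. Nor can Section 7.1 be presumed to prevail: Section 6.3 points to the Study Calendar for the frequency and timing of assessments, and Section 9.6 ties data entry to the study calendar in the trial management system.

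**Conclusion.** The inconsistency is real and should be corrected. Footnote t, followed as written, leaves patients below PR who stop before progression without scheduled disease assessment, contrary to Section 7.1. Until progression is confirmed or new therapy starts, it also leaves them without a fixed-interval survival contact. The 4-weekly and 12-weekly call intervals conflict as well.

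The consequence is a modest risk of undated progression and informative PFS censoring in a descriptive secondary analysis. It arises only if sites follow the calendar rather than Section 7.1; if Section 7.1 is followed, these patients are evaluated every 4 weeks. The number affected is not in the documents and is probably small. Neither the size nor the direction of any bias is established. ORR is a best response counted up to treatment discontinuation (Section 2.3), so it, the Simon rule and the power are untouched. DOR is untouched because footnote t covers responders.

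**What to change.** Amend footnote t so that every patient who stops before progression, whatever the response, has the 4-weekly serum disease evaluations of Section 7.1, with the same end points (confirmed progression, death, new myeloma treatment, withdrawal of consent or end of study). In footnote t and Section 6.3, state one survival-contact interval that applies to every patient off treatment, whatever the reason, for 1 year after the last dose. The stopping criteria need no change.

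The cost is a wording amendment, some additional telephone contacts, and routine serum tests in non-responders off treatment that Section 7.1 already requires. It is best done early, since progression dates that were missed may not be recoverable later.
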